Milled golden flaxseed flaxseed provides 1.09 g of dietary fiber per serving, which contributes to improved intestinal motility and helps maintain microbiota balance. Its fatty acid profile ensures the sequential metabolic conversion of oleic acid (omega-9), linoleic acid (omega-6), and alpha-linolenic acid (omega-3) into arachidonic acid, EPA, DHA, and prostaglandins, thereby supporting inflammatory regulation and cerebral blood flow.

Dosage and Administration

Participants will be instructed to take 23 g of the T-2 investigational nutritional formulation, twice daily, dissolved in 250 ml of liquid.

For the study population (Trisomy 21, ASD, and ADD/ADHD), it is recommended that the investigational formulation be prepared with Casein-free beverage, which is casein-free and enriched with probiotic fiber. However, it may also be consumed with other liquids—including cow's milk, plant-based beverages, coffee, tea, water, or natural juice—without altering its properties. The formulation can be taken hot, cold, or warm.

The first daily dose should be consumed upon waking, ideally 30–60 minutes before breakfast. The second dose should be taken in the afternoon, approximately two hours before sleep, regardless of dinner timing.

Ethnography

Studying quality of life (QoL) in families with a member diagnosed with Autism Spectrum Disorders (ASD), Attention Deficit Disorder (ADD/ADHD), or Trisomy 21 (Down Syndrome) is a central aspect of this research. Such analysis makes it possible to assess not only the progress of participants undergoing nutritional intervention but also the broader impact on family dynamics.

In recent years, QoL has gained increasing importance due to the limited opportunities for social, family, and leisure activities, particularly in households managing neurodevelopmental conditions. Evidence from the initial phases of this line of research has demonstrated that nutritional interventions can strengthen specific abilities in individuals with disabilities while also enhancing the overall well-being of their families.

These outcomes justify expanding the scope of investigation from ethnographic exploration to sociological analysis, providing valuable insights into the cognitive and behavioral evolution of participants, as well as the adaptive changes within their families over the course of one year.

Sleep Physiology

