Laboratory Studies

Laboratory support included:

- Blood count: red/white series, platelets, sedimentation.
- Blood chemistry: glucose, urea, creatinine, uric acid, lipids, triglycerides.
- C-reactive protein: marker of inflammation.
- Serum homocysteine: marker of fat metabolism and oxidative stress.
- Plasma cortisol: indicator of adrenal activity.
- Thyroid panel: T4, free T4, T3, protein-bound iodine, TSH, total cholesterol.

- Stool analyses: coprological, coproparasitoscopic (3 samples).

Some specialized biochemical analyses were conducted at The Great Plains Laboratory (Kansas, USA), led by [name], including:

- IgG Food Allergy Panel (93 foods).
- Comprehensive Organic Acid Test (65 metabolites).
- Urinary peptides from gluten and casein.

Anthropometrics

Weight, height, and BMI were measured monthly, compared against WHO growth standards (BMI-for-age) and Mexican NOM references (NOM-008-SSA2-1993; NOM-174-SSA1-1998).

Ethnography

The study adopted a longitudinal approach using the Sherlock model, combining quantitative and qualitative assessments of personal, functional, and social quality of life. Families underwent three structured interviews (baseline, mid-study, final), recorded in audio and video, with statistical and content analysis applied to results.

Neuropsychology

IDEA Inventory (ASD): Applied to establish severity, guide interventions, and assess treatment impact across 12 dimensions.

Down Syndrome: Cognitive assessments emphasized daily life skills, cognitive processes, and emotional capacities. Recommended tests were culturally and linguistically adapted (Rondal, Perera & Spiker, 2011; Edgin et al., 2010). Tools included:

- **Ages 3–6:** BATELLE developmental inventory (Newborg et al., 1998).
- **Ages 6–35:** NEUROPSI Attention and Memory (Ostrosky et al., 2003), Executive Function Battery (Flores et al., 2008, 2011), computerized neuropsychological tasks (Ostrosky et al., 2003), basic emotion recognition tasks, Barthel Index (Cid-Ruzafa & Damián-Moreno, 1997), and BRIEF executive function scale (Goia et al., 2000).

The neuropsychological evaluation was coordinated by [name] [name], with support from trained psychology interns (4–6 students).

ADD: NEUROPSI Attention and Memory (6–85 years), EDAH (for ADHD), and Conners' Scales (long parent version, 80 items) were applied.

Polysomnography and P300

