- Lic. [name] – Project Administrator (CONACYT CVU: 499625)
- I.B. [name] – Biomedical Area Leader (CONACYT CVU: 353604)
- [name] [name] – Neurobiology Area Leader (CONACYT CVU: 39694)
- [name] [name] – Neuropsychological Evaluation for Down Syndrome (CONACYT CVU: 174346)
- Lic. [name] – Neuropsychological Evaluation for ADD (CONACYT CVU: 510484)
- [name] – Ethnographic Area Leader (CONACYT CVU: 510634)

Institutional Site

Instituto Mexicano de Medicina Integral de Sueño

Associated Entities

- Mexico: Olarte y Akle Bacteriólogos, S.A. de C.V.
- United States: The Great Plains Laboratory, Inc.

- Integración Down, I.A.P.
- Domus Instituto de Autismo

PROGRESS CONTROL PLAN

The project is scheduled to last 13 months, from December 2021 to December 2022, and will be divided into two stages of approximately six months each.

Stage I: Design and Intellectual Property Protection

Duration: First Semester

Objectives:

- Confirm the physiological and metabolic similarities documented in the literature across the study populations and design a unified nutritional intervention scheme.
- Determine expected cerebral modifications resulting from the intervention by standardizing the protocol in neurotypical animal models.

Goals:

- Create a homogeneous information base documenting physiological and metabolic affinities among the target populations.
- Obtain audiovisual records of families highlighting quality of life aspects.
- Establish a specialized dataset on sleep habits of individuals with the studied neurodevelopmental disorders.
- Document neuropsychological and behavioral profiles within family, social, and school contexts.

Activities:

- **Bimonthly 1:** Confirm study populations (Down Syndrome, ASD, ADD).
- Assign dietary subgroups (Pilot, Diet, Control).
- Conduct studies of the T-2 investigational nutritional formulation
- Baseline studies including laboratory tests, clinical reviews, anthropometric measures, ethnographic interviews, neuropsychological tests, full polysomnographic records, and P300 potentials.

- Standardize animal model protocol.
- **Month 1:** Start nutritional intervention (diet implementation).
- **Month 4-6:** Report baseline results, documenting biomedical, dietary, familial, cognitive, behavioral, and sleep-related findings. Conduct behavioral tests in animal models.

Expected Results at the End of Stage I (6 months):

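### Could the diet start in Month 1 mean that some baseline assessments are taken on the diet?

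*Protocol*

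**What the plan says.** The Protocol's Progress Control Plan is the only part of the document that dates these activities. It sets the calendar: "The project is scheduled to last 13 months, from December 2021 to December 2022", divided into "two stages of approximately six months each".

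The Stage I activities open with "Bimonthly 1: Confirm study populations (Down Syndrome, ASD, ADD". Undated bullets follow: assignment to Pilot, Diet and Control, studies of the T-2 formulation, "Baseline studies including laboratory tests, clinical reviews, anthropometric measures, ethnographic interviews, neuropsychological tests, full polysomnographic records, and P300 potentials", and standardization of the animal protocol. The next dated entries are "Month 1: Start nutritional intervention (diet implementation" and "Month 4-6: Report baseline results".

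The protocol does not define Bimonthly 1 or say from when Month 1 is counted. It gives the T-2 formulation no start date separate from the diet. No sentence requires a participant's baseline assessments to be complete before that participant's first day on the diet.

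The Stage II activities then plan comparisons of baseline with follow-up. Under Population Segregation in the Methodology, Pilot and Diet follow the dietary protocol and Control does not.

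**The concern.** Bimonthly most naturally means a two-month block. Counted from project start, the first block is months 1 and 2, and Month 1 lies inside it. Taken literally, the schedule starts the diet while baseline assessments are still open.

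A value measured on the diet is not a true baseline. If the diet acts early, such a value absorbs part of the effect, and later change looks smaller. Only Pilot and Diet could be affected, so their change relative to Control would be distorted, most likely downwards. One baseline measure is plausibly sensitive to recent intake: Laboratory Studies lists "Urinary peptides from gluten and casein". The Metabolism section of the background attributes such peptides to incomplete digestion of those food proteins, and the family seminars cover gluten-free eating. This is an inference, because the document does not list what the diet excludes.

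**Working it through.** No sample size, power or error rate is involved, and the plan states no figure to reproduce. The check is a comparison of calendar labels.

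**Inputs** (Progress Control Plan unless stated): a 13-month project from December 2021 to December 2022; Stage I of about 6 months; baseline studies listed under Bimonthly 1; diet start in Month 1; baseline report in Month 4-6; 72 participants estimated under Population Description, or 27 + 25 + 24 = 76 from Table 1.

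**1. Both labels counted from project start, two-month block.** Bimonthly 1 is December 2021 to January 2022, and Month 1 is December 2021. The windows overlap. The longest time on the diet at the last baseline assessment is 2 minus the start time in months:
- start on the first day: 2 - 0 = 2 months
- start at the end of Month 1: 2 - 1 = 1 month
- start at the end of the block: 2 - 2 = 0 months

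The first two figures are upper limits. For any participant assessed before starting, the figure is 0 whatever the calendar month.

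**2. Month 1 counted from the end of the block.** There is no overlap. If both Month entries share that clock, Month 4-6 becomes project months 4 + 2 = 6 to 6 + 2 = 8, which overruns a six-month Stage I by up to 2 months. This reading is possible but strained.

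**3. Bimonthly read as twice a month.** The block is about 15 days and can end before the diet starts within Month 1. Full sleep recordings would then run at 72/15 = 4.8 to 76/15 = 5.1 a night at one clinic, against 72/30 = 2.4 to 76/30 = 2.5 over a whole month. Clinic capacity is not given, so neither rate settles the matter.

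**4. The one-year remark.** The Ethnography part of the Justification speaks of "the adaptive changes within their families over the course of one year". If that were a year on the diet, 13 - 12 = 1 month would remain for everything else, and a two-month block first would need 2 + 12 = 14 months. But the phrase describes how families evolve, and a year counted from the baseline interview fits any order of baseline and diet. It does not separate the readings.

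**5. Does overlap of the windows contradict a clean baseline?** No. Month 1 says when the intervention begins, and the two-month label says when a set of activities is done. Both hold if participants are assessed in turn and each starts after assessment. Three features support that order:
- the baseline bullet comes before the diet start in the list;
- the assessments are called baseline throughout and are set against follow-up in Stage II;
- the Neuropsychology section uses the autism inventory to establish severity and steer the intervention, which it can do only if applied beforehand.

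**6. Which comparisons would be exposed?** The Stage II goals test the hypothesis by comparing supplemented with non-supplemented groups. Within that, Pilot against Diet is largely protected, because both arms follow the diet on the same schedule. Comparisons of follow-up values alone are also largely unaffected. Change from baseline in Pilot or Diet against Control is what remains exposed.

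**The case for a change.** The strongest case for a change is that visit order relative to the intervention belongs in a protocol and is not usually left to an analysis plan. Here the only dated schedule prints two undefined labels that collide on their most natural reading. The readings that avoid overlap are weaker: one pushes a Stage I report past the end of Stage I, and the other compresses the sleep studies into about two weeks. List order and the word baseline show intent but do not bind any participant. A sentence fixing the order would cost almost nothing.

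Much of this stands. The labels are undefined, the two-month reading from project start is the most natural one, and no rule is written for the individual participant. It does not follow that the plan is wrong. The overlap itself rests on list position, since the baseline bullet carries no date of its own. Even granting it, the labels are compatible with the ordinary sequence, and no text suggests that anyone intended or accepted a baseline measured on the diet.

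The Polysomnography and P300 section also says that participants had dietary support throughout, without excepting Control. How that squares with the Control definition is a separate question of wording with no bearing on when baseline was measured.

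**Conclusion.** The concern does not call for a change. The schedule is loosely labelled, but it does not contradict itself, and the unwritten step, baseline before each participant's own start, is one that competent investigators and analysts take for granted.

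From the printed labels, time on the diet at the last baseline assessment is bounded between 0 and 2 months on the reading least favourable to the plan, and is 0 if the ordinary sequence was followed. The resulting bias cannot be sized from the document. It would arise only if overlap actually occurred, and would fall mainly on change against Control.

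This conclusion assumes that baseline has its usual meaning and that assessment dates and each participant's diet start can be read from study records, so that an analyst could recognise a late value. The second point is normal practice but is not stated in the protocol. Evidence that assessments were in fact done after the diet began would reopen the question. The document contains none.
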